Study weeks 0-2 —Study Drug Titration: Following completion of baseline assessments, participants will be randomized 1:1 to prazosin or placebo. The initial dose will be 1 mg prazosin or placebo capsule taken at bedtime for 2 nights. The first dose of prazosin/placebo will be taken while the participant is in bed for the night to avoid orthostatic syncope, an uncommon but recognized “first dose” effect of prazosin or any alpha-1 antagonist if started at a high dose. The first dose effect is avoidable by starting treatment with a low dose (1 mg before bedtime) and then titrating the dose upward gradually. Such titration avoids excessive blood pressure reduction.

The participant will be asked to call the study team the morning after the first dose to make sure there was no occurrence of postural dizziness. If there have not been any adverse events, the participant will be instructed to increase the dose to 1 mg three times per day (morning, afternoon and bedtime) on the third day. The participant will be given 24-hour contact number in case of adverse events when the dose is increased. However, in our prior study of prazosin in AUD, there has been no problem with this dose increase.

Participants will undergo 2 additional titration visits (weeks 1 and 2). At each titration visit, seated /supine and standing BP and HR will be measured, and presence of side effects and/or adverse events will be assessed. Concomitant medications and health status will be updated. The alcohol use calendar will be administered at every study visit. P

Mid-week titration increases will occur if the participant does not experience any unacceptable side effects. A 24-hour contact number will be provided should any adverse events occur at any time.

A dose increase will occur if the participant does NOT have unacceptable side effects. Clinical judgement may be used to maintain or decrease the dose as necessary. If the participant has intolerable side effects during the titration period, the dose will be reduced to the previous titration step. The dose may be re-challenged if clinically appropriate.

Titration will proceed according to the following schedule:

Study Drug Dose Schedule

		AM	MIDDAY	BEDTIME
Week 0/BL	Days 1-2			1 mg
	Days 3-4	1 mg	1 mg	1 mg
	Days 5-7	2 mg	2 mg	2 mg
Week 1	Days 8-10	2 mg	2 mg	6 mg
	Days 11-14	4 mg	4 mg	6 mg
Week 2	Days 15-21	4 mg	4 mg	8 mg
Week 3	Days 22-end of study	4 mg	6 mg	10 mg

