The titration schedule and target dose were chosen based on clinical experience in treating PTSD with prazosin and on our initial study for AUD in which this titration schedule was well tolerated.¹⁵ Typical, effective, and well-tolerated doses of prazosin in Veterans with PTSD treated at VA Puget Sound range between 5-30 mg/day.⁷⁷ In our prior work with prazosin, study participants have tolerated without difficulty abrupt discontinuation of these doses of prazosin with no need for tapered withdrawal.

Weeks 3-5: If participants delay titration for any reason (e.g., dose maintained and not increased due to temporary AE), the dose may be increased/adjusted through week 5. No dose changes will be allowed after week 5. If titration is required, procedures noted for weeks 1-2 (above) will be followed. If no titration is required, procedures for weeks 6-13 (below) will be followed.

Weeks 6-13: Participants will be asked to return at weeks 6, 7, 8, 9, 11, and 13. At each visit, vital signs, including orthostatic BP and HR, will be measured. Side effects and/or adverse events (if any) will be monitored by open-ended AE reporting and the Adverse Symptom Checklist which includes symptoms which may be attributable to prazosin (e.g., lightheadedness, dizziness on standing, palpitations, drowsiness, headache, nausea, lack of energy, weakness, depressed mood). For vital signs parameters, hypotension will be defined as systolic BP < 90 and clinically meaningful orthostatic hypotension defined as ≥ 20 mmHg drop in systolic BP accompanied by lightheadedness or syncope. If the participant develops an unacceptable adverse effect considered related to study drug, downward dose adjustment will be made.

Concomitant medications and health status will be updated.

The alcohol use calendar will be administered at every study visit. Outcome assessments (CAPS, PCL-M, PHQ-9, PACS, SIP, PSQI) will be administered at weeks 8 and 13.

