drink units per day and binge drinking days throughout the trial, which will serve as primary outcome measures.

- *The Penn Alcohol Craving Scale (PACS)*: A self-report paper-and-pencil instrument that assesses various dimensions of craving for alcohol and has been found to have good reliability and validity.⁸¹ The PACS will be administered at baseline and on weeks 8, 13 and 19, and will be used as a primary outcome measure to determine whether prazosin is associated with reductions in alcohol craving.
- *Alcohol Use Disorders Identification Test (AUDIT)*:⁸² A 10-item self-report questionnaire that has served as a screening instrument for alcohol problems in a number of different settings.⁸³ The AUDIT measures at least two factors, one related directly to alcohol consumption and the other to adverse behavioral effects of excessive consumption.^{84, 85} An advantage of the AUDIT is that it can delineate not just individuals likely to have an alcohol use disorder diagnosis but can place respondents on the full spectrum of alcohol misuse from no problem to hazardous drinking to dependence. The AUDIT has well supported reliability, validity, sensitivity, and specificity. The AUDIT will be modified to inquire about the past year, and will be administered at baseline. The AUDIT will be used to characterize the sample.
- *Clinician-Administered PTSD Scale for DSM-IV (CAPS)*:⁸⁶ The 17-item CAPS uses a structured clinical interview designed to assess the 17 symptoms of PTSD outlined in the DSM-IV. The CAPS will be used by the interviewer to make a current (past month DSM-IV diagnoses of PTSD. The frequency and intensity of each symptom on the CAPS is rated on separate 5-point scales, yielding both dichotomous and continuous scores (range = 0 to 8) for each symptom and for the disorder as a whole (range = 0 to 136). The CAPS will be used as a stratification variable for group assignment and as a secondary outcome measure and will be administered at screen, baseline (to be done at baseline only if more than 14 days has elapsed since the screen visit) and weeks 8, 13 and 19.

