- *Pittsburgh Sleep Quality Index (PSQI)*⁸⁷: A self-report questionnaire assessing sleep quality and disturbances over a 1-month time interval. Nineteen individual items generate seven subscale scores: subjective sleep quality, sleep latency, sleep duration, habitual sleep efficiency, sleep disturbances, use of sleeping medication, and daytime dysfunction. A global score may be obtained by summing the seven component subscales (total score range: 0-21). The PSQI will be used as a secondary outcome measure and will be completed at baseline and weeks 8, 13 and 19.
- *Short Inventory of Problems (SIP)*:⁸⁸ This 15-item self-report questionnaire will be used to assess problems with alcohol, other than alcohol dependence. The SIP has been found to have adequate test-retest reliability and internal consistency. The SIP will be used as a secondary outcome measure to determine whether prazosin is associated with reductions in alcohol-related problems. This self-report instrument will be completed at baseline and weeks 8, 13 and 19.
- *PTSD Checklist-Military (PCL-Military)*:⁸⁹ A well validated 17-item self-report measure assessing severity of PTSD symptoms specifically in the military combat operations context consistent with DSM-IV criteria, with scores ranging from 17 to 85. The PCL-M will be completed at baseline and weeks 8, 13 and 19.
- *Patient Health Questionnaire-9 (PHQ-9)*:⁹⁰ The 9-item depression module of the Patient Health Questionnaire, a self-report version of the PRIME-MD used to diagnose major mental disorders. The PHQ-9 items correspond with DSM-IV criteria for depression, with each item scored from "not at all" to "nearly every day." Items of the PHQ-9 are internally consistent (alpha = 0.86-0.89) and the questionnaire exhibits high test-retest reliability coefficients. Agreement between the PHQ-9 and clinician-based interview diagnosis of major depression is high, with a sensitivity of 88% and a specificity of 88% using a PHQ-9 score ≥ 10 . The PHQ-9 will be completed at baseline and weeks 8, 13 and 19.

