11.0 Statistical/Data Analysis Plan

11.1 Statistical Considerations:

List the statistical methods to be used to address the primary and secondary objectives, specific aims, and/or research hypotheses. Explain how missing data and outliers will be handled in the analysis. The analysis plan should be consistent with the study objectives. Include any sub-group analyses (e.g., gender or age group). Specify statistical methods and variables for each analysis. Describe how confounding variables will be controlled in the data analysis

Primary Outcome Measures: Analysis of the primary outcomes will follow the ITT principal. For each of the two outcomes, a linear regression model with covariates that include treatment group, the stratifying variables, and baseline value of the outcome will be used to compare the prazosin and placebo groups at 13 weeks. In addition, we will conduct a repeated measures analysis using data from the two points of follow-up (8 and 13 weeks). The repeated measure analysis will be conducted by comparing response profiles between prazosin and placebo groups. An initial comparison will be conducted using the general estimating equations (GEE) method of Liang and Zeger,⁹¹ which allows all observed data points for each participant. Secondarily, an analysis of covariance (ANCOVA) rate of change analysis will be done as a confirmatory or sensitivity analysis. Stratifying variables will be included as covariates in each model since they are factors in the stratification. It is anticipated that a retrieved dropout strategy will

result in a limited number of missing observations. For the GEE analysis no imputation strategy is required. For the ANCOVA analysis the missing data patterns will be evaluated between the treatment groups. If the patterns are similar and the magnitude of missing data is small, a conventional last observation carried forward (LOCF) imputation will be performed. If the amount of missing data is substantial and/or the patterns of missingness disparate, as an alternative to the traditional ANCOVA, the summary statistic method of Dawson⁹² will be employed. This method has been shown to be robust to non-ignorable missingness. The approach summarizes the response profile using a least square slope, and stratifies on the missing data pattern. We will also run analyses to assess the interactions between treatment group and gender.

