A completers analyses will be done in a similar fashion for the primary outcome measures, using only the cases that remained on protocol throughout the 13-week study drug period.

Secondary outcome measures: All secondary outcome measures (PSQI, CAPS, PCL-M, SIP, and biological markers) will be analyzed in a manner similar to that described above for the primary outcome measures. (We will also perform exploratory analyses in a similar manner on the CAPS symptom clusters and individual CAPS items to generate hypotheses about differential responsiveness to prazosin for AUD relative to response of individual PTSD symptom clusters/symptoms).

Procedures to minimize missing data: Although all efforts will be made to complete study visits in person, it may be necessary to obtain assessments by telephone. Attempts will be made to reach the participant by telephone. The following actions will be attempted (as appropriate per visit schedule): 1) adverse events will be assessed by telephone, 2) assessments shall be completed by telephone interview with the raters, 3) self-rated measures will be done by mail using prepaid envelopes, and 4) dispensing of study drug shall be done by traceable shipment. No-show, missed visits and actions taken will be documented in the study record.

11.2 Sample Size:

Sample Size Estimation: The power analysis is based on two types of preliminary data: the results of [name] study of prazosin for reduction of alcohol use in persons with AUD without PTSD and the preliminary results of our study of prazosin for combat trauma PTSD in active duty SMs without AUD in which we obtained the PACS. There were 19 completers in [name] pilot study. Standard drink units in the final month of the study drug period were 30.3 ± 32 (mean \pm SD) ($N=10$) in the prazosin group and 62 ± 58 ($N=9$) in the placebo group ($F=1.50$, $p=0.012$). There were 53 completers in the prazosin study for combat trauma PTSD in active duty SMs. The difference (delta) in PACS scores were -2.6 ± 5.8 ($N=27$) vs. -0.3 ± 3.3 ($N=26$) in the prazosin vs. placebo groups, respectively, $t=-1.74$, $p=0.04$ (one-tailed).

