Study Discontinuation or Termination: If the participant is not able to tolerate a minimum dose of 3 mg /day of placebo/prazosin, he or she will undergo early termination and all week 13 assessments will be performed; the participant will be referred to his/her primary mental health care provider for further management. Reasons for early discontinuation or withdrawal will be recorded.

Participants may be discontinued prematurely from study treatment to manage deterioration of clinical status. Specifically, dangerousness toward self or others or emergence of acute psychiatric symptoms necessitating hospitalization will result in discontinuation from the study. If at any time during the study, psychiatric symptoms become markedly increased resulting in severe participant distress or presenting immediate danger to self or others, the participant will be discontinued from the study. In case of need for increased level of care or emergent care, study personnel will provide a warm hand-off to DBH personnel. DBH personnel will assume responsibility for arranging appropriate care.

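### Week-13 assessments done at early termination for intolerance can fall in the titration weeks, and the plan neither says how they enter the 13-week comparison nor schedules a later outcome contact

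*Combined protocol and SAP*

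**What the plan says.** Section 13.6 deals with participants who cannot tolerate a minimum of 3 mg/day of blinded study drug. For such a participant, "he or she will undergo early termination and all week 13 assessments will be performed", followed by referral.

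Section 10.1 fixes how early that can be. If the first dose causes no trouble, the participant is told to "increase the dose to 1 mg three times per day (morning, afternoon and bedtime) on the third day", which is the first time 3 mg/day is reached. If titration is delayed, "the dose may be increased/adjusted through week 5". The same section gives the certificate of appreciation at the week-19 visit or at the early discontinuation visit, and ends access to medical records 30 days after completion or early discontinuation. It schedules no outcome contact after early termination.

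Section 11.1 follows the intention-to-treat principle. For each primary outcome, a linear regression "will be used to compare the prazosin and placebo groups at 13 weeks". A GEE analysis uses weeks 8 and 13, and a rate-of-change ANCOVA serves as a sensitivity analysis. On dropouts the section says: "It is anticipated that a retrieved dropout strategy will" leave few observations missing. The strategy is not described. For missed visits, the section allows that "assessments shall be completed by telephone interview with the raters" and that self-rated forms be sent by mail.

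Section 10.2 has the alcohol use calendar cover the time since the last visit. Two secondary measures look back a month: the CAPS ("The CAPS will be used by the interviewer to make a current (past month DSM-IV diagnoses of PTSD") and the PSQI ("A self-report questionnaire assessing sleep quality and disturbances over a 1-month time interval"). It gives no recall period for the PACS.

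**The concern.** An assessment made in week 1 or 2 is not a 13-week outcome, whatever its form is called. The plan has no visit window and no rule for assigning an early-termination value to a time point, which leaves two readings.

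- **The exit battery is analysed as week 13.** A titration-period value then stands in for the primary outcome. It also counts as observed, which hides missingness that Section 11.1 uses to choose between LOCF and the summary-slope method. In the rate-of-change analysis, a change over about 2 weeks would be spread over 13.
- **The exit battery is left out.** These randomised participants then have no week-13 outcome, because none is scheduled.

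The trigger is drug intolerance, so either problem plausibly falls more heavily on prazosin. All participants also receive alcohol treatment. If drinking and craving fall in both arms over the trial, an early value misses most of that fall, and the first reading would bias the comparison against prazosin.

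**Working it through.** **The plan's own figures (Section 11.2).** With s = √((s₁² + s₂²)/2) and power = Φ(Δ/(s√(2/n)) − 1.96) at n = 60 per arm:

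- PACS: Δ = 2.6 − 0.3 = 2.3; s = √((5.8² + 3.3²)/2) = 4.72; power 76.1% two-sided (stated 76%) and 84.7% one-sided (stated 85%).
- Standard drink units: Δ = 62 − 30.3 = 31.7; s = √((32² + 58²)/2) = 46.84; power 96.0% (stated 97%).
- Number randomised: 120/(1 − 0.40) = 200, as stated.

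These reproduce closely, so the point does not turn on a wrong figure.

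**Timing of the exit.** The dose is 1 mg three times daily on days 3–4, so 3 mg/day can first fail in week 1. Adjustment runs through week 5, so the exit can also be later. Both are well short of week 13.

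**What the exit values measure.** At week 2, about half of a one-month look-back (CAPS, PSQI) precedes randomisation. The calendar at that visit covers days since the last visit, all after baseline. For the PACS the documents do not allow a statement. Titration-period values is therefore the accurate description for the primary calendar.

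**Possible shift if exit values are scored as week 13.** Assume a common fall F in PACS over 13 weeks, linear in time, exits at week t, and exit shares p₁ (prazosin) and p₀ (placebo). The arm difference shifts against prazosin by

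(p₁ − p₀) × F × (13 − t)/13.

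The documents give neither share, and Section 14.1 gives no placebo rates. The only placebo PACS change in the documents is −0.3, in Service Members without diagnosed AUD.

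- 15% v 5%, F = 0.3, t = 2: 0.10 × 0.3 × 11/13 = 0.025 points, 1% of 2.3.
- 15% v 5%, F = 5, t = 2: 0.10 × 5 × 11/13 = 0.42 points, 18% of 2.3.
- 15% v 5%, F = 5, t = 5: 0.10 × 5 × 8/13 = 0.31 points, 13% of 2.3.
- 2% v 1%, F = 5, t = 2: 0.01 × 5 × 11/13 = 0.04 points, 2% of 2.3.

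The exit shares and the 5-point fall are assumptions. Dilution because these participants stopped the drug is a separate matter: an intention-to-treat value taken on the true week-13 date could carry it too.

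**The case against.** The strongest reply is that Section 13.6 says which assessments are done at exit, not how they are analysed, and that Section 11.1 already foresees retrieving dropouts. The first part is right. A reader might infer that the 13-week comparison does take in early values, but no section says so. The defect is a missing rule together with a missing later contact. The second part does not answer the point. The only outcome assessment described for these participants is the one on the day of exit, and the telephone and mail procedures are written for missed visits. The expectation of few missing observations also sits uneasily with the 40% dropout assumed in Section 11.2.

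Other stronger readings also fail:

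- A reader might infer that the exit values are mostly pre-treatment. That does not hold for the calendar and cannot be shown for the PACS.
- A reader might infer that these participants are counted as finished. Section 11.6 requires at least 10 of the 14 interim visits and the 13-week visit, so a week-2 exit is a non-completer.
- A reader might infer a material bias from the adverse-reaction rates in Section 14.1, such as dizziness at 10.3%. Those are not rates of failing 3 mg/day. Section 10.1 reports no problem at this dose step in the prior AUD study, calls the schedule well tolerated, and reduces the dose first when effects are intolerable. Exits may be few.

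It is also fair to object that later data have their own weakness. Under Section 14.6 the blind is broken at termination, and open-label prazosin may follow.

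**Conclusion.** The point holds as a gap in the plan, not as a demonstrated bias. The exit-day battery is a stated rule, the exit can come in the titration weeks, no later outcome contact is scheduled, and the retrieved-dropout strategy has no procedure behind it. The 13-week intention-to-treat comparison may therefore receive a mistimed value, or none, from participants selected by drug intolerance.

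More such exits on prazosin is an inference, and the direction of bias depends on a common fall over time. Under the assumed 15% v 5% exits at week 2, the shift runs from about 0.03 PACS points (common fall 0.3) to about 0.4 (common fall 5), and it is smaller still if exits are rare. The change is worth making because it is cheap and the outcome cannot be recovered afterwards. No view is taken on the 3 mg/day threshold or on the termination rule.

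**What to change.** Leave the termination rule unchanged.

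- **Section 13.6:** call the assessments at termination an exit battery and record the actual study week. Also collect the alcohol use calendar, PACS and other self-report or interview outcomes on the original week-8 and week-13 dates counted from randomisation, by telephone or mail where needed, unless consent is withdrawn.
- **Section 11.1:** define this collection as the retrieved-dropout strategy. State that exit-battery values are not entered as week-13 values and do not count as observed week-13 data when missingness is assessed. Record any open-label prazosin use after termination. Reconcile the expected small amount of missing data with the 40% dropout in Section 11.2.

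The cost is protocol wording and one or two contacts per early exit, using procedures already in the plan. Some participants will decline. Self-report after termination will come from people who know their allocation, although raters stay blind, and the report should say so. PEth and GGT need blood, so they will be missing unless the participant attends in person.
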